7.9.1.6 Healthcare utilization secondary endpoints

The following healthcare utilization secondary endpoint data will be collected for both of the CEAP 2-5 Randomized Studies:

1. Rate of adjunctive treatments conducted through 12 months post-index procedure.

Hypothesis

There is no formal hypothesis test for this study objective.

Endpoint Definition

Rate of adjunctive procedures, phlebectomy or sclerotherapy, for varicosity on the target limb through 12 months post index procedure.

Analysis Methods

The number and rate of adjunctive procedures through 12 months will be estimated by study arm. To calculate the rate, the numerator is the count of adjunctive procedures. The denominator is the number of person-years of follow-up. The amount of follow-up per person is defined as their date of exit or last known follow-up or the date of their 12 month follow-up visit (whichever is first) minus their date of index procedure. A similar estimate will be constructed for the type of adjunctive procedure, phlebectomy or sclerotherapy.

Determination of Subjects for Analysis

The analysis will consist of the ITT population.

2. Healthcare utilization related to the target limb Venous Reflux Disease (VRD), as determined by the number of healthcare visits conducted, between study visits through 60 months (through 12 months for VenaSeal vs. Surgical Stripping Study).

Hypothesis

The following hypothesis will be tested:

$$H_0: r_A = r_C$$

$$H_a: r_A \neq r_C$$

Where r_A and r_C are the rates of healthcare utilization in the VenaSeal™ system arm and the ETA or surgical stripping arm, respectively.

Endpoint Definition

Rate of healthcare utilization visits related to venous reflux disease.

Analysis Methods

The number and rate of healthcare utilization visits will be estimated by study arm. To calculate the rate, the numerator is the count of HCU visits. The denominator is the number of person-years of follow-up. The amount of follow-up per person is defined as their date of exit or last known follow-up minus their date of index procedure. A similar estimate will be constructed within the HCU type of interest (Inpatient, Outpatient, Clinic, Outpatient ER visits).

Determination of Subjects for Analysis

The analysis will consist of the ITT population.

3. Procedures, tests, and treatment of AEs related to the treatment modality or index procedure through 60 months (through 12 months for VenaSeal vs. Surgical Stripping Study).

Hypothesis

There is no formal hypothesis test for this study objective.

Endpoint Definition

Healthcare utilization measured by number of healthcare resources utilized for treatment of adverse events, including hospitalization, prolongation of hospitalization, actions taken or diagnostic tests performed.

Analysis Methods

A listing will be provided per adverse event of the actions taken.

Determination of Subjects for Analysis

The analysis will consist of the ITT population.

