10.2. Scheduled Follow-up Visit Windows

The target visit dates for the subject that gets enrolled in the study can be obtained via 'Visit Scheme' CRF from the study database. Should a subject miss a visit or if the visit falls outside of the pre-specified window, a study deviation must be reported, and the original follow-up schedule should be maintained for subsequent visits.

Data analyses include follow-up visits, regardless of whether the visit occurs within the window. Therefore, a late visit is preferred over a missed visit but must be accompanied by a deviation report. Follow-up visit windows are listed in **Table 8** and **Table 9** and are based on days post-procedure.

Table 8: Follow-up Visit Window – All Subjects, VenaSeal vs Surgical Stripping Study will follow this schedule to 12 months

Study Follow-up Visit	Window (Calculated days post index procedure)		
	Window Start (days post- procedure)	Target (days post- procedure)	Window End (days post- procedure)
Day 7	5	7	9
Day 30	23	30	37
6 Months	154	182	210
12 Months	309	365	421
24 Months	674	730	786
36 Months	1039	1095	1151
48 Months	1404	1460	1516
60 Months	1769	1825	1881

Table 9: Additional Follow-up Visit Window – VLU Study

Study Follow-up Visit	Window (Calculated days post index procedure)		
	Window Start (days post-procedure)	Target (days post-procedure)	Window End (days post-procedure)
2 Months	53	60	67
3 Months	83	90	97
4 Months	113	120	127
5 Months	143	150	157
8 Months	226	240	254
10 Month	286	300	314

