5.1 Study Design

The study design is a global, post-market, prospective, multi-center, randomized-controlled study of patients with symptomatic superficial venous disease, with a single-arm embedded ulcer group. The study is designed with two Randomized Studies (VenaSeal vs. Surgical Stripping Study and VenaSeal vs. ETA Study) for CEAP 2-5 subjects and one single arm active VLU Study for CEAP 6 subjects. Each study will be individually assessed and analyzed for the overall study objectives.

There will be approximately 500 subjects enrolled in the VenaSeal Spectrum Study. Approximately 375 subjects will be enrolled in CEAP clinical classifications 2-5 in the Randomized Studies (108 subjects in VenaSeal vs. Surgical Stripping Study and about 264 subjects in VenaSeal vs. ETA Study), and up to 125 CEAP 6 subjects with VLUs will be treated with the VenaSeal™ system.

Enrollment of the VenaSeal vs. Surgical Stripping Study was closed on 22-Feb-2022. All subjects participating in the VenaSeal vs ETA Study or in the VLU Study (CEAP 2-6) will be followed up to 60 months post-index procedure, all subjects participating in the VenaSeal vs. Surgical Stripping Study will be followed up to 12 months post-index procedure.

Enrollment will take place at up to 40 sites globally.

To avoid introduction of bias to the study results due to disproportionate enrollment, enrollment at any individual site shall not exceed 20% of any single study (approximately 50 subjects for the Randomized Studies and 25 subjects for the VLU Study, excluding screen failures) of the total sample size. It is expected that sites enroll a minimum of 10 subjects per individual study the site is participating in. Enrollment was halted early for the VenaSeal vs. Surgical Stripping study, so control of each site's contribution to the overall total was not possible.

Randomization will be stratified by study site and CEAP classification 2/3 vs. 4/5. There is no blinding in this study. The detailed procedure of randomization information is described in the Randomization and Blinding Plan separately.

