5.2 Duration

It is anticipated that enrollment will take approximately 36 months following enrollment of the first subject. The estimated study duration is approximately 8 years, including up to 60-month follow-up post-procedure and excluding the time required for preparing the final report. The expected duration of each subject's participation is up to 60 months after the index procedure, apart from subjects who were enrolled in the VenaSeal vs. Surgical Stripping Study. The latter will be followed through 12-months only.

Data will be recorded in the Case Report Form (CRF) at screening, baseline, index procedure (day 0), and during follow-up at 7 days (\pm 2 days), 30 days (\pm 7 days), 6 months (\pm 4 weeks), 12 months (\pm 8 weeks), 24 months (\pm 8 weeks), 36 months (\pm 8 weeks), 48 months (\pm 8 weeks) and 60 months (\pm 8 weeks).

Additional routine care visits can be conducted to accommodate adjunctive procedures 3 or more months following the index procedure (data for adjunctive procedures will be collected through 60 months), per the treating physician's discretion; these will not be considered study visits.

Data of subjects who were enrolled in the VenaSeal vs. Surgical Stripping Study will be recorded in the CRF at screening, baseline, index procedure (day 0), and during follow up at 7 days (\pm 2 days), 30 days (\pm 7 days), 6 months (\pm 4 weeks), and 12 months (\pm 8 weeks).

CEAP 6 subjects will have additional study visits until healing verification and data will be recorded in the CRFs at: 2 months (\pm 7 days), 3 months (\pm 7 days), 4 months (\pm 7 days), 5 months (\pm 7 days), 8 months (\pm 2 weeks), 10 months (\pm 2 weeks). If the healing has not occurred by 12 months, subjects will continue to follow standard wound care and remaining study visits. Subjects will come in for ulcer healing verification visits up to 24 months, after which no core laboratory ulcer assessment for wound healing will be required.

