7.1 Study Subjects

7.1.1 Disposition of Subjects

The number and percentage of subjects screened, enrolled, received therapy and completed each scheduled clinical follow-up visit will be summarized. The number and percentage of subjects who complete the study and who exit early will be summarized by exit reason as documented on the case report form (CRF). The subject clinical follow-up compliance will be provided at each study visit by study arm via a flow diagram and/or table.

The VenaSeal vs. Surgical Stripping Study was originally planned to have 5 years of subject follow-up. However, in CIP version 4.0, the follow-up was reduced to 12 months and the endpoints were updated accordingly. It is likely that some subjects will collect data beyond 12 months during transition of the CIP change. Data collected beyond 12 months will be reported in listings. If there is a sufficient sample size for some endpoints, these endpoints may also be summarized.

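### The 12-month adjunctive-procedure rate has no fixed cap on person-time, so an ETA or VLU subject who misses the 12-month visit but stays in follow-up adds multi-year exposure against a 12-month count

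*SAP*

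**What the plan says.** SAP 7.9.1.6 item 1 sets the horizon: "The number and rate of adjunctive procedures through 12 months will be estimated by study arm". It then gives the formula: "To calculate the rate, the numerator is the count of adjunctive procedures", divided by person-years. Each subject's person-years run from the index procedure to "their date of exit or last known follow-up or the date of their 12 month follow-up visit (whichever is first"). SAP 7.9.2.5 item 1 uses the same formula for the VLU Study. No hypothesis test is attached in either place.

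Follow-up length differs by study. Under SAP 5.1, ETA and VLU subjects "will be followed up to 60 months post-index procedure". For the Stripping Study, SAP 5.2 states: "The latter will be followed through 12-months only". SAP 7.1.1 adds a qualification for that study: "It is likely that some subjects will collect data beyond 12 months during transition of the CIP change".

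Protocol 10.2 deals with missed and late visits. After a missed visit, "the original follow-up schedule should be maintained for subsequent visits". Visits outside the window are kept: "Data analyses include follow-up visits, regardless of whether the visit occurs within the window". The 12-month window in Protocol Table 8 is days 309 to 421, with day 365 as target.

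**The concern.** A rate needs its events and its exposure to cover the same interval. Here the events are limited to 12 months. Exposure is limited to 12 months only if the subject attended a 12-month visit, exited, or was last seen by then. A subject with no 12-month visit has no visit date to enter into the minimum, so exposure runs on to exit or last follow-up. The protocol foresees such subjects: someone who misses a visit stays on schedule, and Protocol 10.17.6 prefers reduced data collection to exit.

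The SAP caps exposure elsewhere. Its Kaplan-Meier endpoints (for example 7.9.1.2.4, and 7.9.1.5 item 2) also censor at the analysis time point. That cap is absent here. At stake is a named healthcare-utilization endpoint, reported by arm, that could be diluted, and in the ETA Study diluted unequally between arms.

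**Working it through.** The documents state no rate, no person-time and no share of missed 12-month visits, so there is no figure of the plan's own to reproduce. The check applies the SAP rule as written.

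Inputs from the documents:
- Protocol Table 8: 12-month target day 365, 24-month target day 730, 60-month target day 1825, 60-month window end day 1881, 12-month window end day 421.
- SAP 5.1: about 264 subjects in the ETA Study, so 264/2 = 132 per arm.

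Assumed, because the documents do not give it: *s*, the share who miss the 12-month visit but stay in follow-up. All other subjects are set to 1 year of exposure, and the numerator is limited to 12 months.

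**One subject who misses the visit.** Followed to day 1825: 1825/365 = 5.00 years, an excess of 4.00 over the first year. Followed to day 1881: 1881/365 = 5.15 years, an excess of 4.15.

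**Effect on the rate.** With *L* the years of exposure for such a subject, mean person-years per subject are (1 − s) + s·L. The rate relative to one capped at day 365 is 1/[(1 − s) + s·L].

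| s (assumed) | L = 5 (60 months) | L = 2 (24 months) |
|---|---|---|
| 1% | 1/1.04 = 0.96 | 1/1.01 = 0.99 |
| 2% | 1/1.08 = 0.93 | 1/1.02 = 0.98 |
| 5% | 1/1.20 = 0.83 | 1/1.05 = 0.95 |

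At s = 5% and L = 5, one ETA Study arm goes from 132 to 132 × 1.20 = 158.4 person-years with no matching events.

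**Arm difference, ETA Study.** If true rates are equal but 2% skip in one arm and 5% in the other, both followed to 60 months, the apparent rate ratio is 1.20/1.08 = 1.11. The split is illustrative; nothing in the documents indicates one.

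**Stripping Study.** If follow-up ends by day 421, L = 421/365 = 1.153. Even at s = 10% the relative rate is 1/(0.90 + 0.1153) = 0.985.

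**With a fixed cap.** A subject who misses the visit contributes at most 1.00 year, and the relative rate is 1.00 for any s.

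**The case against.** The strongest reply is that the clause was plainly meant to stop exposure at 12 months. Item 2 of the same section, a 60-month endpoint, leaves it out. If the visit date is read as the scheduled target date, which the Visit Scheme CRF supplies for every subject (Protocol 10.2), a missed visit still has a date and the cap holds. The intention is credible, but the SAP does not say this, and a programmer following the text would use the recorded visit date.

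A second reply is that true skipping may be rare. The window is eight weeks either side, a late visit is preferred to a missed one, and a late visit still supplies a date. This stands as a limit on size: at 1% skipping the rate is 0.96 to 0.99 of its correct value.

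A third is that consequences are small. The endpoint is descriptive and drives no alpha, sample size or claim. The count of procedures is reported beside the rate, and SAP 7.1.1 reports visit compliance by arm, so a reader could see missed visits. All of that stands.

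A fourth concerns the numerator, since the formula sentence does not repeat the 12-month limit. The endpoint definition and the preceding sentence both carry it. Were the numerator unrestricted, subjects without a 12-month visit would add later procedures as well, and the result would not be a 12-month rate. The text needs correction either way, but the downward direction depends on the 12-month limit.

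A reader might also infer that the 309 to 421 day window is a separate error, because the visit date seldom equals day 365. The documents do not support that. The SAP often expresses its 12-month horizon as the 12-month visit; if that is meant here, events and exposure match for everyone who attends.

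**Conclusion.** The rule as written is wrong for one kind of subject: an ETA or VLU subject with no 12-month visit who remains in follow-up. For that subject a 12-month count is set against as much as about 5 years of exposure, about 4 of them in excess. The rate is then understated, by 4% to 17% for an assumed 1% to 5% skipping with follow-up to 60 months, or by 1% to 5% with follow-up to 24 months. If nobody skips, the bias is zero.

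Three stronger readings are tempting and should not be drawn. One is that the reported rate will be too low: the documents give no skip share, so only the gap in the rule is certain. Another is that each such subject adds five years of error: the first year belongs in the denominator. The third is that the comparison between arms is biased across the trial: the VLU Study has one arm, and Stripping Study follow-up stops at about 12 months, with any transition data beyond that assigned mainly to listings. A false arm difference is possible only in the ETA Study, and only if skipping differs by arm. This is worth correcting, in proportion to a descriptive secondary endpoint.

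**What to change.** In SAP 7.9.1.6 item 1 and 7.9.2.5 item 1, cut numerator and denominator at the same fixed time point. Count procedures on or before day 365, and end person-time at the earlier of day 365 and exit or last known follow-up. This follows the analysis-time-point cap already used for the SAP's Kaplan-Meier endpoints. As a secondary benefit, a fixed day also removes any mismatch from the spread of 12-month visit dates. The cost is one line of text in each item and the matching line of programming; no new data are needed.

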7.9.1.7 Patient Experience secondary endpoints

1. Time to return to normal activities as reported by the patients.

Hypothesis

For time to return to normal activities, the following hypothesis will be tested:

$$H_0: S_A(t) = S_C(t)$$

$$H_a: S_A(t) \neq S_C(t)$$

Where $S_A(t)$ and $S_C(t)$ are the survival functions for freedom from return to normal activities for the VenaSeal™ system arm and ETA or surgical stripping arm, respectively.

Endpoint Definition

Time to return to normal activities as reported by the patients.

Analysis Methods

For the return to normal activities endpoint, a Kaplan-Meier survival estimator will be used to estimate the survival functions for both the VenaSeal™ and the control arm (i.e., ETA or Surgical Stripping). A cumulative incidence figure will be produced to compare the two treatments. An event occurs when a patient indicates at a follow-up visit that they have returned to normal activities. The censoring time is the time to study exit, the later of either the last contact date or the discontinuation date, or the time point for analysis, whichever comes first. A log-rank test will be used to test whether the survival distributions differ between the treatment groups. If a patient is reported to have returned to normal activities, but the date of return is unknown, the return date will be imputed from the date of the follow-up visit. For those who have returned to normal activities, the median, Q1, Q3, minimum, and maximum will summarize the number of days to return to normal activities, as well as the number who have not returned to normal activities in each treatment arm.

Determination of Subjects for Analysis

The analysis will consist of the ITT population.

2. Intra-procedural and post-procedural pain at the index procedure, and 7 days and 30 days as reported by the patient using the numeric rating scale (NRS) with a scale of 0-10.

Hypothesis

There is no formal hypothesis test for this study objective.

Endpoint Definition

Pain is reported by the patient using a scale ranging from 0-10.

Analysis Methods

The total pain values at baseline, at each visit will be summarized within each treatment arm. In the VenaSeal vs. Surgical Stripping study, the pain information will further be summarized within types of anesthesia received during the procedure.

Determination of Subjects for Analysis

The analysis will consist of randomized subjects that underwent a procedure.

3. Change in venous disease symptoms at 7 and 30 days, and at 6, 12, 24, 36, 48, and 60 months compared to baseline (7 and 30 days, 6 and 12 months only for VenaSeal vs. Surgical Stripping Study), as measured by the revised Venous Clinical Severity Score (rVCSS) and subject self-reporting.

Hypothesis

The following hypothesis will be tested:

$$H_0: \mu_A(t) - \mu_A(0) = \mu_C(t) - \mu_C(0)$$

$$H_a: \mu_A(t) - \mu_A(0) \neq \mu_C(t) - \mu_C(0)$$

where $\mu_A(t)$ and $\mu_C(t)$ are the mean VCSS scores at time point t in the VenaSeal™ system arm and the ETA or surgical stripping arm, respectively. Time t is any of 7 days, 30 days, 6, 12, 24, 36, 48, or 60 months.

Endpoint Definition

The VCSS is a validated 10-question venous disease severity measurement intended to evaluate the responses to changes in disease severity over time and in response to treatment. Each signs / symptom can have a grade ranging from 0 (absent) to 3 (severe). The total VCSS score is the sum of all questions. The score ranges from 0 (no venous disease) to 30 (severe venous disease).

Analysis Methods

The total VCSS value at baseline, at each visit, and change from baseline will be summarized for ITT population. The comparison will be done between the VenaSeal and control (ETA or Surgical Stripping) arms. In order to test the above stated statistical hypothesis, a Wilcoxon two-sample test with t approximation will evaluate the change in the score index from baseline to time t. The analysis will be performed using SAS code similar to:

```
proc npar1way data= vcsschg Wilcoxon plots = none;
  title "Wilcoxon test of Change in VCSS scores";
  class trtGroup;
```

```
var vcssdiff;  
where cpevent="XXX";  
run;
```

Additionally, a linear mixed effects model will be fit on VCSS scores with an interaction variable fit for time and study group. Time points include baseline and scheduled follow-up visits. The model will account for the correlation of scores within each subject. Likelihood ratio tests will be used to test for the significance of the study group effect and the time effect. Partial t-tests will be used to compare scores between study groups at specific time points.

The analysis will be performed using SAS code similar to:

```
PROC MIXED;  
  CLASS time trtGroup;  
  MODEL VCSS = time trtGroup time*trtGroup;  
  RANDOM INT / SUBJ=ptid corr=exch;  
RUN;
```

Determination of Subjects for Analysis

The analysis will consist of the ITT population.

4. Change in AVVQ score at 30 days, and 6, 12, 24, 36, 48, and 60 months (30 days, 6 and 12 months only for VenaSeal vs. Surgical Stripping Study) compared to baseline.

Hypothesis

The following hypothesis will be tested:

$$H_0: \mu_A(t) - \mu_A(0) = \mu_C(t) - \mu_C(0)$$

$$H_a: \mu_A(t) - \mu_A(0) \neq \mu_C(t) - \mu_C(0)$$

where $\mu_A(t)$ and $\mu_C(t)$ are the mean AVVQ scores at time point t in the VenaSeal™ system arm and the ETA or surgical stripping arm, respectively. Time t is any of 7 days, 30 days, 6, 12, 24, 36, 48, or 60 months.

Endpoint Definition

The AVVQ (Aberdeen Varicose Vein Questionnaire) is a validated, venous-disease specific QoL measure including 13 questions that each correspond to one of four clinically recognizable aspects of health, being 1) pain and dysfunction, 2) cosmetic appearance, 3) extent of varicosity, 4) complications [Garratt AM et al 1993]. The total score of AVVQ is the sum of all questions and ranges from 0 to 100 for each leg.

Scores are computed if at least half the items are completed within the instrument, i.e., if 7 or more questions are missing, the overall score is also set to missing. If a question is omitted by a patient the total possible score for that question is subtracted from the maximum possible score for the questionnaire. This way a score out of 100 can still be calculated by dividing the total score by the new maximum possible and multiplying by 100. For patients suffering from varicose veins in both legs, but

missing responses for a question divided into left and right legs, the entire question is set to missing. For questions divided into left and right legs, some patients suffering from varicose veins in only one leg have a tendency to miss out boxes for the unaffected leg, rather than ticking the first box implying no symptoms. As a rule, if a patient misses any of the response set for one leg and having completed question 1 has not drawn in any varicose veins on the same leg, their missing responses for that one leg should be coded as zero i.e. no symptoms. Question 4 of the AVVQ was not asked in this study and therefore is excluded from the scoring. Because this question is missing, the maximum possible score is 97.783. Calculating the modified AVVQ to account for missing questions uses the following adjustment: Score = 100 * [Patient Score] / [Max Possible Score] where Patient Score is the sum of the answered questions. The scoring instructions for the AVVQ are located in the Statistical Appendices.

Analysis Methods

The total AVVQ value at baseline, at each visit, and change from baseline will be summarized for ITT population. The comparison will be done between the VenaSeal and control (ETA or Surgical Stripping) arms. In order to test the above stated statistical hypothesis, a Wilcoxon two-sample test with t approximation will evaluate the change in the score index from baseline to time t.

Determination of Subjects for Analysis

The analysis will consist of the ITT population.

5. Change in EuroQoL Group 5-Dimension Self-Report Questionnaire (EQ-5D-5L) at 30 days, and 6, 12, 24, 36, 48 and 60 months (30 days, 6 and 12 months only for VenaSeal vs. Surgical Stripping Study) compared to baseline.

Hypothesis

The following hypothesis will be tested:

$$H_0: \mu_A(t) - \mu_A(0) = \mu_C(t) - \mu_C(0)$$

$$H_a: \mu_A(t) - \mu_A(0) \neq \mu_C(t) - \mu_C(0)$$

where $\mu_A(t)$ and $\mu_C(t)$ are the mean EQ-5D scores at time point t in the VenaSeal™ system arm and the ETA or surgical stripping arm, respectively. Time t is any of 7 days, 30 days, 6, 12, 24, 36, 48, or 60 months.

Endpoint Definition

The EQ-5D is a two-component tool consisting of a descriptive part that evaluates five dimensions (mobility, self-care, usual activities, pain/discomfort, anxiety/depression) and the EQ-VAS, a vertical, visual analog scale, used for self-reporting on health. The EQ-5D index can be calculated based on the EQ-5D-5L crosswalk from the US TTO value set. Guidance is on the EuroQol Group website (EQ-5D- 5L Value Sets): <https://euroqol.org/wp-content/uploads/2021/01/EQ-5D-5LUserguide-08-0421.pdf>.

Analysis Methods

The EQ-5D index and visual analog scale (VAS) values at baseline, at each visit, and change from baseline will be summarized for ITT population. The comparison will be done between the VenaSeal and control

(ETA or Surgical Stripping) arms. In order to test the above stated statistical hypothesis, a Wilcoxon two-sample test with t approximation will evaluate the change in the score index from baseline to time t.

Determination of Subjects for Analysis

The analysis will consist of the ITT population.

6. Change in the 36-Item Short Form Health Survey (SF-36) reported by the patient at 30 days, and 6 and 12 months compared to baseline.

Hypothesis

The following hypothesis will be tested:

$$H_0: \mu_A(t) - \mu_A(0) = \mu_C(t) - \mu_C(0)$$

$$H_a: \mu_A(t) - \mu_A(0) \neq \mu_C(t) - \mu_C(0)$$

where $\mu_A(t)$ and $\mu_C(t)$ are the mean SF-36 physical or mental health scores at time point t in the VenaSeal™ system arm and the ETA or surgical stripping arm, respectively. Time t is any of 7 days, 30 days, 6, or 12 months.

Endpoint Definition

The SF-36 is a 36-item generic QoL tool measuring health across three dimensions and including eight separate scales: 1) Functional status (including physical functioning, social functioning, role limitations attributed to physical problems, and role limitations attributed to emotional problems), 2) wellbeing (including mental health, energy and fatigue, and pain), and 3) overall evaluation of health (including general health perception). This study will report the results of the physical functioning and mental health scales.

Analysis Methods

The SF-36 physical functioning and mental health scales at baseline, at each visit, and change from baseline will be summarized for ITT population. The comparison will be done between the VenaSeal and control (ETA or Surgical Stripping) arms. In order to test the above stated statistical hypothesis, a Wilcoxon two-sample test with t approximation will evaluate the change in the scales from baseline to time t.

Determination of Subjects for Analysis

The analysis will consist of the ITT population.

7. Change in the Venous Dependent Quality of Life (VenousDQoL) reported by the patient at 30 days, and 6, 12, 24, 36, 48, and 60 months (30 days, 6 and 12 months only for VenaSeal vs. Surgical Stripping Study) compared to baseline.

Hypothesis

There is no hypothesis test for this endpoint.

Endpoint Definition

Subjects answer their general quality of life with potential responses on an ordinal scale as follows: excellent, very good, good, neither good nor bad, bad, very bad, or extremely bad. Subjects also answer what their quality of life would be without varicose veins with potential responses on an ordinal scale as follows: very much better, much better, a little better, the same, or worse.

Analysis Methods

For each treatment arm and time point, the count and percentage of subjects with each response will be presented.

Determination of Subjects for Analysis

The analysis will consist of the ITT population.

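### The additional rVCSS mixed model compares raw scores visit by visit and gains nothing from the collected baseline; baseline should be used for adjustment, with a covariance that lets it differ from follow-up

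*SAP*

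**What the plan says.** SAP 7.9.1.7 item 3 states a null hypothesis of equal mean change from baseline in the two arms at each visit. The test it assigns to that hypothesis is rank-based: "a Wilcoxon two-sample test with t approximation will evaluate the change in the score index from baseline to time t".

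A second analysis follows: "Additionally, a linear mixed effects model will be fit on VCSS scores with an interaction variable fit for time and study group". On the role of baseline the SAP says "Time points include baseline and scheduled follow-up visits". The example code, offered as code similar to what will be run, has the fixed effects "MODEL VCSS = time trtGroup time*trtGroup" and the covariance statement "RANDOM INT / SUBJ=ptid corr=exch". Two kinds of test are named: "Likelihood ratio tests will be used to test for the significance of the study group effect and the time effect", and "Partial t-tests will be used to compare scores between study groups at specific time points".

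The code has no statement defining a contrast and sets no reference visit. It has no baseline covariate and does not constrain the arm means at baseline. SAP 7.9.1.3 leaves p-values for these secondary endpoints unadjusted for multiplicity.

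**The concern.** In a model with time, arm and their interaction, and with baseline as a level of time, every arm-by-visit mean is free, including the two baseline means. The difference in scores at a follow-up visit is then estimated from that visit alone when data are complete. Baseline rVCSS is measured in every subject under the schedule, but it neither corrects a chance imbalance nor sharpens the comparison.

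There are three practical consequences. The model's visit results and the Wilcoxon results on change may disagree only because they estimate different contrasts. The arm-effect test includes a visit at which treatment cannot yet have acted. And precision is given up, which matters most in the stripping study, closed at 108 subjects.

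**Working it through.** The documents give no power, effect size or correlation for rVCSS, so there is no planned figure to reproduce. Correlations and effects below are assumptions, shown as ranges.

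**Inputs**
- Arm sizes at 1:1 (SAP 5.1): 264/2 = 132 (ETA study) and 108/2 = 54 (stripping study).
- Visits (SAP 7.9.1.7 item 3): baseline plus 8 follow-ups, T = 9 (ETA); baseline plus 4, T = 5 (stripping).
- SDs (Protocol 4.1, single-centre single-arm post-market study): 2.4 at baseline, 1.4 at 1 and 3 months.
- Assumed: correlation rho of 0.3, 0.5 or 0.7; arm effect d of 0.4 SD, constant after baseline; two-sided 5% level.

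**1. What the visit test estimates.** The SAP's model was fitted to simulated complete data. At the first follow-up visit:
- model contrast: -0.42424
- raw mean difference: -0.42424
- model contrast with baseline rows deleted: -0.42424
- difference in change: -0.43527, returned only by the interaction coefficient taken against baseline

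The generalised least squares variance with and without baseline rows has ratio 1.0000. With 10% monotone dropout, having baseline in the model lowers the variance by 0.3 to 0.8% (ETA) or 0.5 to 1.6% (stripping); with 30% dropout, by at most 4.5%.

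**2. What adjustment would give.** Relative to the raw contrast, with a correctly modelled covariance, the variance is 1 - rho²: 0.91, 0.75 or 0.51. Single-visit power is Φ(d/SE - 1.96), with SE = √(2/n) raw and √(2(1 - rho²)/n) adjusted, in SD units.

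| Study | n per arm | Raw | rho 0.3 | rho 0.5 | rho 0.7 |
|---|---|---|---|---|---|
| ETA | 132 | 90.1% | 92.6% | 96.3% | 99.5% |
| Stripping | 54 | 54.7% | 58.7% | 67.0% | 82.9% |

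**3. Why not simply switch to change.** With equal SDs, change has 2(1 - rho) times the raw variance: 1.40, 1.00 or 0.60. With the SDs in Protocol 4.1 the ratio is (2.4² + 1.4² - 2·rho·2.4·1.4)/1.4² = (7.72 - 6.72·rho)/1.96 = 2.9, 2.2 or 1.5. Adjustment does better than both at every rho examined.

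**4. The arm-effect test.**
- *Main-effect form.* Baseline has weight 1/T, so a constant d shrinks to 8/9 d (ETA) or 4/5 d (stripping). Stripping power is 70.8%, 57.4% or 47.9% with baseline in the average, and 85.4%, 74.8% or 65.6% over follow-up visits only.
- *Joint form (all arm terms dropped).* Nothing is averaged. The noncentrality equals that of the baseline-constrained test, and the only cost is 5 df instead of 4 (or 9 instead of 8). Stripping power is 73.6%, 74.9% or 87.0%, against 77.2%, 78.4% or 89.5%.

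**5. The covariance matters for the repair.** Suppose the baseline means are made equal but the exchangeable structure is kept. The visit estimate is then the raw difference minus b times the baseline difference, where b is the fitted common correlation (average covariance over average variance). With k = 2.4/1.4 = 1.714, its true variance relative to raw is 1 - 2·b·rho·k + b²k².
- Stripping: the average variance is (5.76 + 4·1.96)/5 = 2.72. The average covariance is rho(4·3.36 + 6·1.96)/10 = 2.52·rho, so b = 0.926·rho. At rho = 0.5, b = 0.463 and the ratio is 1 - 0.794 + 0.631 = 0.84, a 16% gain.
- Across rho 0.3, 0.5 and 0.7 the gain is 6%, 16% and 32% (stripping) and 5%, 15% and 29% (ETA), not 9%, 25% and 49%.
- If the correlation is 0.3 from baseline to follow-up but 0.6 between follow-ups (assumed), then for stripping b = (4·0.3·3.36 + 6·0.6·1.96)/10/2.72 = 0.408. The ratio is 1 - 0.419 + 0.488 = 1.07, a 7% loss. The same steps for ETA give an 18% loss.

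An unstructured covariance estimates the baseline slope directly and restores the rho-squared gain.

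**The case against.** The strongest reply is that the stated hypothesis already has its own test. The SAP ties the Wilcoxon test on change to it by name and introduces the mixed model only as additional. A reader might infer that rVCSS change is left without a matching test; the text does not support that, and no multiplicity-controlled claim rests on the model.

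Second, the change contrast is inside the model: it is the interaction measured against baseline, and the phrase partial t-tests could mean tests of coefficients. This stands only in part. The sentence says scores at specific time points, and no reference visit is set, so the literal reading is a comparison of scores.

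Third, a reader might infer that the arm effect is certainly diluted by 1/9 or 1/5. The documents do not establish this. The SAP names a likelihood ratio test without saying which terms are dropped, and the joint form involves no averaging, only one extra degree of freedom.

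Fourth, equal baseline means are not guaranteed by design here. Protocol 10.4 places randomization before baseline data collection, the trial is unblinded, and rVCSS is staff-assessed and includes pain and use of compression (Protocol 10.5 and Appendix A). This objection stands and shapes the fix.

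**Conclusion.** The point holds as a low-severity improvement to a supplementary analysis. Read literally, the rVCSS mixed model tests raw visit differences. With complete data baseline contributes nothing to them, and with dropout of up to 30% it contributes at most 4.5% of variance. Baseline also enters the arm-effect test in a form the SAP leaves open.

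The available gain is about rho squared in variance, provided the covariance lets baseline differ from follow-up. It would be wrong to infer that equalising the baseline means is enough on its own: with the only SDs in the documents and the SAP's exchangeable structure, the gain is smaller and can turn into a loss.

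The powers rest on an assumed 0.4 SD effect, assumed correlations and complete data. The SDs come from one single-arm study. Late-visit numbers will be lower, since remote 48- and 60-month visits omit rVCSS (Protocol 10.10). The loss matters mainly in the stripping study.

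**What to change.** Keep the Wilcoxon test on change as the test of the stated hypothesis. Amend the mixed model as follows.

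1. Use baseline rVCSS for adjustment, in one of two ways: (a) keep baseline as a response with one common mean for both arms and put arm-by-visit terms only at follow-up visits; or (b) model post-baseline scores with baseline and baseline-by-visit as covariates.
2. Replace the exchangeable structure with an unstructured covariance. At the least, under option (a), give baseline its own variance and its own covariance with follow-up.
3. Define the arm-effect test as a joint test of the follow-up arm-by-visit terms, and report each term with a 95% confidence interval.
4. State the assumption that baseline rVCSS is unaffected by the assigned arm, tabulate the baseline arm means, and report the unconstrained difference-in-change contrast as a sensitivity analysis.

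The cost is SAP wording and a modest code change, with no new data. The drawbacks are more covariance parameters, mainly at nine time points in the ETA study, and reliance on a baseline taken after open-label randomization, which item 4 makes visible.
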